7.2.2 Reporting of Pregnancy and Lactation to the Study Chair and to Merck

Although pregnancy and lactation are not considered adverse events, it is the responsibility of investigators or their designees to report any pregnancy or lactation in a subject (spontaneously reported to them), including the pregnancy of a male subject’s female partner that occurs during the trial or within 120 days of completing the trial completing the trial, or 30 days following cessation of treatment if the subject initiates new anticancer therapy, whichever is earlier. All subjects and female partners of male subjects who become pregnant must be followed to the completion/termination of the pregnancy. Pregnancy outcomes of spontaneous abortion, missed abortion, benign hydatidiform mole, blighted ovum, fetal death, intrauterine death, miscarriage and stillbirth must be reported as serious events (Important Medical Events). If the pregnancy continues to term, the outcome (health of infant) must also be reported.

Such events must be reported within 24 business hours to the Study Chair and within 2 business days to Merck Global Safety, from the time of investigator awareness. See Appendix 11.7.

7.2.3 Immediate Reporting of Adverse Events to the Study Chair, Merck, and the FDA

7.2.3.1 Serious Adverse Events

A serious adverse event is any adverse event occurring at any dose or during any use of either investigational product (GM-CSF and/or pembrolizumab) that:

- Results in death;
- Is life threatening;
- Results in persistent or significant disability/incapacity;
- Results in or prolongs an existing inpatient hospitalization;
- Is a congenital anomaly/birth defect;
- Is a new cancer (that is not a condition of the study);
- Is associated with an overdose.

Refer to Table 6 for additional details regarding each of the above criteria.

Any serious adverse event, or follow up to a serious adverse event, including death due to any cause other than progression of the cancer under study that occurs to any subject from the time the consent is signed through 90 days following cessation of treatment, or the initiation of new anti-cancer therapy, whichever is earlier, whether or not related to either or both investigational products, must be reported within 24 business hours to the Study Chair and within 2 business days to Merck Global Safety, from the time of investigator awareness. See Appendix 11.7.

Additionally, any serious adverse event, considered by an investigator who is a qualified physician or health care professional to be related to either or both investigational products that is brought to the attention of the investigator at any time outside of the time period specified in the previous paragraph also must be reported immediately to the Study Chair and to Merck in the same manner as SAEs.

All subjects with serious adverse events must be followed up for outcome.

7.2.3.2 Protocol-Specific Exceptions to Serious Adverse Event Reporting

Efficacy endpoints as outlined in this section will not be reported to Merck as described in Section 7.2.3.- Immediate Reporting of Adverse Events to Study Chair, Merck, and FDA, unless there is evidence suggesting a causal relationship between the drug and the event.

Specifically, the suspected/actual events covered in this exception include any event that is related to or caused by disease progression of the cancer under study.

Hospitalization related to convenience (e.g., transportation issues, etc.) also will not be considered a SAE.

The Study Chair will monitor unblinded aggregated efficacy endpoint events and safety data to ensure the safety of the subjects in the trial. Any suspected endpoint which upon review is not

progression of the cancer under study will be forwarded to Merck Global Safety as a SAE within 2 working days of determination that the event is not progression of the cancer under study.

7.2.3.3 IND Safety Reporting to FDA

UCSF will report to the FDA all IND reportable events occurring in patients enrolled on this study using FDA Form 3500A (MedWatch, Appendix 11.7). Reportable events must meet the definition in Federal Regulations (21 CFR §312.32):

- Suspected adverse reaction (defined as a reasonable possibility that the investigational agent caused the adverse event)
- Unexpected (not listed in the investigator brochure or package insert(s), or is not listed at the specificity or severity that has been observed)
- Serious (as defined in 7.2.3.1)

If the adverse event does not meet all three of the definitions, it should not be submitted as an expedited IND safety report. The timeline for submitting an IND safety report to FDA is no later than 15 calendar days after the Investigator determines that the suspected adverse reaction qualifies for reporting (21 CFR 312.32(c)(1)). Any unexpected fatal or life-threatening suspected adverse reaction will be reported to FDA no later than 7 calendar days after the Investigator's initial receipt of the information (21 CFR 312.32(c)(2)).

Any relevant additional information that pertains to a previously submitted IND safety report will be submitted to FDA as a Follow-up IND Safety Report without delay, as soon as the information is available (21 CFR 312.32(d)(2)).

A copy of all 15 Day Reports and Annual Progress Reports will be submitted as required by FDA. Investigators will cross-reference this submission according to local regulations to the Merck Investigational Compound Number (IND) at the time of submission. Additionally, investigators will submit a copy of these reports to Merck & Co., Inc. (Attn: Worldwide Product Safety; [contact]) at the time of submission to FDA.

7.2.4 Evaluating Adverse Events

An investigator who is a qualified physician or health professional (e.g., Nurse Practitioner) will evaluate all adverse events according to the NCI Common Terminology for Adverse Events (CTCAE), version 4.0. Any adverse event which changes CTCAE grade over the course of a given episode will have each change of grade recorded on the adverse event case report forms/worksheets.

All adverse events, regardless of CTCAE grade must also be evaluated for seriousness.

Table 6 Evaluating Adverse Events

An investigator, who is a qualified physician or health care professional, will evaluate all adverse events as to:

V4.0 CTCAE Grading	Grade 1	Mild; asymptomatic or mild symptoms; clinical or diagnostic observations only; intervention not indicated.
	Grade 2	Moderate; minimal, local or noninvasive intervention indicated; limiting age-appropriate instrumental ADL.
	Grade 3	Severe or medically significant but not immediately life-threatening; hospitalization or prolongation of hospitalization indicated; disabling; limiting self-care ADL.
	Grade 4	Life-threatening consequences; urgent intervention indicated.
	Grade 5	Death related to AE
 Seriousness	A serious adverse event is any adverse event occurring at any dose or during any use of Merck product that:	
	† Results in death; or	
	† Is life-threatening; or places the subject, in the view of the investigator, at immediate risk of death from the event as it occurred (Note: This does not include an adverse event that, had it occurred in a more severe form, might have caused death.); or	
	† Results in a persistent or significant disability/incapacity (substantial disruption of one's ability to conduct normal life functions); or	
	† Results in or prolongs an existing inpatient hospitalization (hospitalization is defined as an inpatient admission, regardless of length of stay, even if the hospitalization is a precautionary measure for continued observation. (Note: Hospitalization [including hospitalization for an elective procedure] for a preexisting condition which has not worsened does not constitute a serious adverse event.); or	
	† Is a congenital anomaly/birth defect (in offspring of subject taking the product regardless of time to diagnosis); or	
	Is a new cancer; (that is not a condition of the study) or	
	Is an overdose (whether accidental or intentional). Any adverse event associated with an overdose is considered a serious adverse event. An overdose that is not associated with an adverse event is considered a non-serious important medical event and must be reported within 24 hours.	
	Other important medical events that may not result in death, not be life-threatening, or not require hospitalization may be considered a serious adverse event when based upon appropriate medical judgment, the event may jeopardize the subject and may require medical or surgical intervention to prevent one of the outcomes listed previously (designated above by a †).	
Duration	Record the start and stop dates of the adverse event. If less than 1 day, indicate the appropriate length of time and units	
Action taken	Did the adverse event cause the Merck product to be discontinued?	
Relationship to test drug	Did the Merck product cause the adverse event? The determination of the likelihood that the Merck product caused the adverse event will be provided by an investigator who is a qualified physician or health care professional. The investigator's signed/dated initials on the source document or worksheet that supports the causality noted on the AE form ensures that a medically qualified assessment of causality was done. This initialed document must be retained for the required regulatory time frame. The criteria below are intended as reference guidelines to assist the investigator in assessing the likelihood of a relationship between the test drug and the adverse event based upon the available information. The following components are to be used to assess the relationship between the Merck product and the AE; the greater the correlation with the components and their respective elements (in number and/or intensity), the more likely the Merck product caused the adverse event (AE):	
	Exposure	Is there evidence that the subject was actually exposed to the Merck product such as reliable history, acceptable compliance assessment (pill count, diary, etc.), expected pharmacologic effect, or measurement of drug/metabolite in bodily specimen?
	Time Course	Did the AE follow in a reasonable temporal sequence from administration of the Merck product? Is the time of onset of the AE compatible with a drug-induced effect (applies to trials with investigational medicinal product)?
	Likely Cause	Is the AE not reasonably explained by another etiology such as underlying disease, other drug(s)/vaccine(s), or other host or environmental factors

Relationship to Merck product (continued)		The following components are to be used to assess the relationship between the test drug and the AE: (continued)	
	Dechallenge	
Was the Merck product discontinued or dose/exposure/frequency reduced?
 
If yes, did the AE resolve or improve?
 
If yes, this is a positive dechallenge. If no, this is a negative dechallenge.
 
(Note: This criterion is not applicable if: (1) the AE resulted in death or permanent disability; (2) the AE resolved/improved despite continuation of the Merck product; or (3) the trial is a single-dose drug trial); or (4) Merck product(s) is/are only used one time.)
	
	Rechallenge	
Was the subject re-exposed to the Merck product in this study?
 
If yes, did the AE recur or worsen?
 
If yes, this is a positive rechallenge. If no, this is a negative rechallenge.
 
(Note: This criterion is not applicable if: (1) the initial AE resulted in death or permanent disability, or (2) the trial is a single-dose drug trial); or (3) Merck product(s) is/are used only one time).
 
NOTE: IF A RECHALLENGE IS PLANNED FOR AN ADVERSE EVENT WHICH WAS SERIOUS AND WHICH MAY HAVE BEEN CAUSED BY THE MERCK PRODUCT, OR IF REEXPOSURE TO THE MERCK PRODUCT POSES ADDITIONAL POTENTIAL SIGNIFICANT RISK TO THE SUBJECT, THEN THE RECHALLENGE MUST BE APPROVED IN ADVANCE BY THE U.S. CLINICAL MONITOR AS PER DOSE MODIFICATION GUIDELINES IN THE PROTOCOL.
	
	Consistency with Trial Treatment Profile	Is the clinical/pathological presentation of the AE consistent with previous knowledge regarding the Merck product or drug class pharmacology or toxicology?	
The assessment of relationship will be reported on the case report forms /worksheets by an investigator who is a qualified physician or health care professional according to his/her best clinical judgment, including consideration of the above elements.			
Record one of the following		Use the following scale of criteria as guidance (not all criteria must be present to be indicative of a Merck product relationship).	
Yes, there is a reasonable possibility of Merck product relationship.		There is evidence of exposure to the Merck product. The temporal sequence of the AE onset relative to the administration of the Merck product is reasonable. The AE is more likely explained by the Merck product than by another cause.	
No, there is not a reasonable possibility Merck product relationship		Subject did not receive the Merck product OR temporal sequence of the AE onset relative to administration of the Merck product is not reasonable OR there is another obvious cause of the AE. (Also entered for a subject with overdose without an associated AE.)	

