7.2 Assessing and Recording Adverse Events

An adverse event is defined as any untoward medical occurrence in a patient or clinical investigation subject administered a pharmaceutical product and which does not necessarily have to have a causal relationship with this treatment. An adverse event can therefore be any unfavorable and unintended sign (including an abnormal laboratory finding, for example), symptom, or disease temporally associated with the use of a medicinal product or protocol-specified procedure, whether or not considered related to the medicinal product or protocol-specified procedure. Any worsening (i.e., any clinically significant adverse change in frequency and/or intensity) of a preexisting

condition that is temporally associated with the use of the investigational product(s), is also an adverse event. Adverse events may occur during the course of the use of the investigational products during the Treatment Period or within the Follow-Up Phase of this study. Progression of the cancer under study is not considered an adverse event unless it is considered to be drug related by the investigator.

The investigational products in this study are pembrolizumab and GM-CSF.

All adverse events will be recorded from the time the consent form is signed through 30 days following cessation of treatment and at each examination on the Adverse Event case report forms/worksheets. The reporting timeframe for adverse events meeting any serious criteria is described in section 7.2.3.

7.2.1 Definition of an Overdose for This Protocol and Reporting of Overdose to the Study Chair and to Merck

For purposes of this trial, an overdose of pembrolizumab will be defined as any dose of 1,000 mg or greater or GM-CSF 1250 µg or greater in a single dose (≥ 5 times the indicated dose). No specific information is available on the treatment of overdose of pembrolizumab. Appropriate supportive treatment should be provided if clinically indicated. In the event of overdose, the subject should be observed closely for signs of toxicity. Appropriate supportive treatment should be provided if clinically indicated.

If an adverse event(s) is associated with (“results from”) the overdose of a Merck product, the adverse event(s) is reported as a serious adverse event, even if no other seriousness criteria are met.

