8.3.2 Secondary Endpoints

- 1) **Safety** endpoint assessment is described in Section 7.2. The safety endpoints are AEs graded using CTCAE (Version 4.0) criteria. Safety will be assessed by quantifying the toxicities and grades experienced by subjects who have received pembrolizumab plus GM-CSF induction, including SAEs and ECIs. Other safety endpoints include laboratory safety assessments, ECOG performance status, Child Pugh score, vital signs, and physical examinations. The incidence and frequency of dose reduction, treatment delays, and discontinuation for lack of tolerability will be quantified. Re-induction and Second Course safety events will be addressed in the same manner.

- 2) **Tumor PD-L1 status** will be measured by IHC and classified as positive or negative by central laboratory testing (QualTek Laboratories) using pre-specified cut-points.
- 3) A key secondary endpoint is %PFS6 (formerly primary endpoint, changed by amendment with addition of Expansion Cohort). For each patient, PFS will be calculated in days and months from date of first dose of protocol therapy to date of first documented radiographic and/or clinical disease progression or death from any cause. For patients removed from study for other reasons than progression or death, PFS will be censored at the date last known to be progression-free. See Section 5.9 for Replacement policy for non-evaluable patients. The %PFS6 will be calculated as the proportion of evaluable patients progression-free at 6 months. Censored patients without progression will be treated as non-progression statistically and counted in denominator toward %PFS6.

For patients who continue on treatment despite radiographic progression based upon impression of clinical benefit an/or assessment with possible pseudo-progression or a delayed response⁴⁶ (see Section 5.8), PFS will be calculated at time of first documented progression after subsequent imaging confirms progression. If subsequent imaging does not demonstrate progression, then a PFS event will not have occurred and the patient will continue with scheduled imaging assessments per protocol to determine PFS.

Re-induction and Second Course PFS (rPFS, sPFS) will be calculated in months from date of first dose of re-induction or Second Course to date of first documented radiographic and/or clinical disease progression during or after re-induction or Second Course, or death from any cause. RPFS and sPFS will be reported descriptively.

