8.4.3 Interim Analyses

8.4.4 Interim Safety Analysis and Stopping Rules

An interim safety analysis was performed after completion of 1st stage enrollment corresponding to approximately 33% enrollment (9 patients in Safety Cohort). The interim safety analysis examined safety during first 3 cycles of treatment (1 cycle single-agent pembrolizumab followed by 2 induction cycles with GM-CSF for total of 9 weeks). If $>20\%$ or more SAE and/or ECI, and/or $>50\%$ Grade ≥ 3 adverse events by NCI CTCAE v.4.0, have occurred during first 3 cycles of treatment and are assessed as both clinically relevant and at least possibly treatment-related, a decision would have been required whether to amend or close the study after the 1st stage. The interim safety analysis showed overall rate of Grade ≥ 3 at least possibly related AE rate of 11%, with 1 related SAE event (11%), meeting criteria to proceed with enrollment to Stage 2 Efficacy Cohort.

The target rate of $\leq 50\%$ at least possibly treatment-related \geq Grade 3 events during the first 3 cycles was conservative based upon rate of 70% for all-cause Grade 3 or 4 toxicity observed with standard first-line chemotherapy in this population,⁹ and treatment-related Grade 3-5 rate of approximately 45% for the combination of ipilimumab plus GM-CSF in advanced melanoma

patients.³⁴ Accrual was placed on hold after the 9th patient was enrolled during 1st stage safety analysis, until at least 8 of the 9 patients had potential to complete 3 cycles (9 weeks) of treatment or had a qualifying safety event. Accrual resumed after completion of safety interim analysis without unexpected safety signals identified.

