3.1 Adverse Event Monitoring

All Grade 3-5 Adverse Events (AEs), whether or not considered to be expected or unexpected and whether or not considered to be associated with the use of the study drug, will be entered into OnCore®, UCSF's Clinical Trial Management System.

Adverse Events are graded according to the Common Terminology Criteria for Adverse Events (CTCAE) (version 4.03) as developed and revised by the Common Therapy Evaluation Program (CTEP) of the National Cancer Institute. Adverse events are further given an assignment of attribution or relationship to treatment or medical procedure.

Attribution categories are:

- Definite – The adverse event is clearly related to the investigational agent(s) or medical procedure.
- Probable – The adverse event is likely related to the investigational agent(s) or medical procedure.
- Possible – The adverse event may be related to the investigational agent(s) or medical procedure.

- Unlikely – The adverse event is doubtfully related to the investigational agent(s) or medical procedure.
- Unrelated – the adverse event is clearly not related to the investigational agent(s) or medical procedure

All Grade 3-5 adverse events entered into OnCore® will be reviewed on a monthly basis at the Site Committee meetings. The Site Committee will review and discuss the selected toxicity, the toxicity grade, and the attribution of relationship of the adverse event to the administration of the study drug(s).

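### Table 6 attributes adverse events to pembrolizumab only, and the plan does not say which attribution scale defines the related Grade 3 or higher rate, so GM-CSF toxicity can be undercounted

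*Combined protocol and SAP*

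**What the plan says.** Section 7.2 is explicit about scope: "The investigational products in this study are pembrolizumab and GM-CSF". Section 7.2.3.1 accordingly defines a serious adverse event by use of either product.

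Table 6 in Section 7.2.4, the form for evaluating each event, is worded for one drug throughout:

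- Seriousness: "A serious adverse event is any adverse event occurring at any dose or during any use of Merck product that" meets one of the listed criteria.
- Action taken: "Did the adverse event cause the Merck product to be discontinued".
- Relationship: a yes/no answer for the Merck product. One prompt is "Is the AE not reasonably explained by another etiology such as underlying disease, other drug(s)/vaccine(s"), and one of the guidance criteria for 'Yes' is "The AE is more likely explained by the Merck product than by another cause".

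The safety hypothesis in Section 3.2 is a related Grade 3 or higher rate of at most 50% for the combination over the first three cycles. Section 8.4.4 applies that limit to events at least possibly related to treatment. Section 8.3.2 refers to Section 7.2 for safety endpoint assessment and adds: "The incidence and frequency of dose reduction, treatment delays, and discontinuation for lack of tolerability will be quantified".

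Appendix 11.1 (item 3.1) has a separate scale: definite, probable, possible, unlikely, unrelated. 'Possible' there means "The adverse event may be related to the investigational agent(s) or medical procedure".

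**The concern.** GM-CSF is the drug this trial adds to pembrolizumab, and the safety question is about the pair. A causality form that names only the partner drug, and treats other drugs as competing explanations, classes the added drug's toxicity as unrelated. A second scale elsewhere in the protocol does cover both agents, but no rule says which one defines 'related'. Two analysts could therefore report different related Grade 3 or higher rates from the same patients and both claim to follow the plan. Any error from using Table 6 would favour the combination.

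**Working it through.** **1. Can 'Merck product' include GM-CSF?** No. Section 9.1.1 has Merck supplying pembrolizumab; Section 9.1.2 has GM-CSF ordered from commercial supply.

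**2. The provisions side by side**

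| Item | Table 6 (7.2.4) | Elsewhere |
|---|---|---|
| Seriousness | use of the Merck product | 7.2.3.1: use of either product |
| Action taken | Merck product discontinued? | 7.1.2.1: action on trial treatment; 8.3.2: reductions, delays and discontinuations |
| Relationship, to what | Merck product | 8.4.4: treatment; 4.3.4: the combination; Appendix 11.1: investigational agent(s); Appendix 11.7: each product |
| Relationship, levels | 2 | Appendix 11.1: 5 |

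**3. A Grade 3 event attributed to GM-CSF.** Take edema or an allergic reaction, both listed in the GM-CSF dose-modification table (Table 4, Section 5.2.2.2). Exposure to pembrolizumab and plausible timing are both met, since the drugs are given in the same cycles. But the conditions for 'No' are joined by 'or', and one is that another cause is obvious. If the investigator judges GM-CSF to be the cause, that condition is met and the entry is 'No'. On the Appendix 11.1 scale the same event would be possible, probable or definite.

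**4. Does Table 6 feed the endpoint?** Section 8.3.2 points to Section 7.2, and Table 6 is the only causality scale there. Table 6 results go on the case report forms or worksheets. Section 8.6.2.1, which describes the safety summaries, does not define 'related'. Section 8 does not cite Appendix 11.1 for attribution. So the literal route leads to Table 6, but no sentence states that the rate is computed from it.

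**5. Action taken.** Section 5.2.2.1 gives no dose-reduction steps for pembrolizumab; the scheduled reductions are in the GM-CSF table. Section 5.2.2 also lets a patient continue pembrolizumab after GM-CSF is stopped for toxicity. The Table 6 item records neither.

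**6. The plan's own figure.** Section 8.4.4 reports an 11% rate in 9 patients and one related serious event. 1/9 = 11.1%, which reproduces it (exact 95% interval 0.3% to 48.2%). With 9 patients, exceeding 50% takes 5 (5/9 = 55.6%), four more than were counted. Exceeding the 20% limit for serious events or events of clinical interest takes 2 (2/9 = 22.2%), one more.

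**7. How much could be lost?** If a fraction f of patients with a related event are recorded as unrelated, the recorded rate is true rate × (1 − f). The documents give no value for f, so f and the true rates here are assumptions. A true 30% would be recorded as 30% × 0.75 = 22.5% at f = 0.25, or 30% × 0.50 = 15% at f = 0.50. The chance that an interim rule with n = 9 is triggered is a binomial tail at that recorded rate:

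| Assumed true rate and trigger | f = 0 | f = 0.10 | f = 0.25 | f = 0.50 |
|---|---|---|---|---|
| Grade 3 or higher 60%, at least 5 of 9 | 0.733 | 0.598 | 0.379 | 0.099 |
| Grade 3 or higher 50%, at least 5 of 9 | 0.500 | 0.379 | 0.217 | 0.049 |
| Related serious events 30%, at least 2 of 9 | 0.804 | 0.745 | 0.636 | 0.401 |

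These show direction and sensitivity only.

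**The case against.** The best defence is that the events behind this endpoint are already attributed on a suitable scale. Appendix 11.1 enters every Grade 3 to 5 event in OnCore whatever its attribution, with a 'possible' category, and has the site committee review them monthly. Section 10.6 makes OnCore the study database. Section 4.3.4 says the interim events were adjudicated against the combination. Section 7.1.2.1 characterizes toxicity by action on trial treatment, not on one product. All of this stands. It means that a reader who infers that GM-CSF toxicity does drop out of the rate goes further than the documents allow: it can drop out, if Table 6 is the source. The case report forms are not in the documents, so what they capture cannot be judged.

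A second tempting reading is that Table 6 rejects any event only possibly due to pembrolizumab. It does not. Its 'Yes' category is a reasonable possibility, and the criteria are guidance that need not all be met. A possible pembrolizumab event with no obvious alternative fits 'Yes', as may one that cannot be separated between the two drugs. The problem is confined to events attributed to GM-CSF.

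Third, the narrower seriousness wording matters little in practice. GM-CSF is given only alongside pembrolizumab, and Section 5.2.2 takes a patient off protocol therapy if pembrolizumab stops permanently, so the exposure periods nearly coincide. Expedited reporting is also worded for both drugs (Section 7.2.3.3, Appendix 11.7).

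What the defence does not supply is a sentence choosing between the scales. Nor does the pooled Appendix 11.1 scale provide the per-product attribution that Appendix 11.7 asks for in MedWatch reports.

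**Conclusion.** Table 6 is wrong as written for a two-drug trial. Followed literally, it records GM-CSF-attributed toxicity as unrelated and does not capture changes to GM-CSF dosing. It conflicts with Sections 7.2, 7.2.3.1 and 8.4.4 and with Appendix 11.1. The plan leaves open which scale defines the related Grade 3 or higher rate. If Table 6 is used, that rate can only be too low on this account.

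The size cannot be estimated: it depends on the share of related events attributed to GM-CSF, which the documents do not give. A reader might infer that the interim 11% is understated or that the decision to continue was unsound. Nothing supports that. The figure reproduces, the adjudication is described as covering the combination, and no missed event is indicated. The limit on serious events was only one patient away, which is a reason to check the records and not evidence of an error.

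**What to change.** - Reword Table 6 to cover pembrolizumab and GM-CSF, and record relationship and action taken (held, reduced, discontinued) separately for each drug. Align its seriousness wording with Section 7.2.3.1.
- State in Sections 8.3.2 and 8.6.2.1 that 'related' means possible, probable or definite on the Appendix 11.1 scale, to either drug, and that this definition serves the Section 3.2 hypothesis and all related-event tables.
- Check the Stage 1 and 2 records (9 + 18 = 27 patients) and re-code from source only those events for which just the Merck-product item was completed.

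The cost is a wording change to one table, a few extra fields on the case report form and a limited record check. The related-event rate may come out slightly higher.
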